### Outcomes

#### Baseline Data

At the beginning of the trial, an initial evaluation was performed to assess the severity of ASD in participants using the CARS score. **Table 1** displays the mean, median, and range of the participant scores. Most participants had moderate to severe ASD, with a CARS score higher than 35. There were no significant differences in age, gender, ethnicity, language status, treatment status, or CARS scores between the Active and Sham groups.

#### Primary Outcome

Every participant who completed the trial was evaluated with CARS post-treatment. There were no missing CARS posttreatment evaluations. In the Active group, the before treatment CARS scores had a mean score value of 43.5 ( $n = 16$ ) with a standard deviation (SD) of 5.7, the after-treatment scores had a mean score of 33.7 with an SD of 5.0. In the Sham group, the before treatment CARS scores had a mean score value of 40.6 ( $n = 14$ ) with SD of 7.2, the after-treatment scores had a mean score of 38.0 with SD of 8.4. **Table 3** shows the mean (M) and SD of the CARS scores for the Active and Sham groups before and after treatment. The difference in the change in CARS between the two groups was 7.23 (95% CI 2.357 to 12.107,  $p=0.01$ ).

In addition to analyzing the changes in CARS scores based on averages, we also conducted respondents-based analyses, quantifying the number of participants in Active and Sham groups, whose change in CARS was greater than 4.5 points (as it has been suggested by Jurek et al 2022 to be the minimal clinically important difference). The result was significant  $\chi^2=8.48$ ,  $p=.004$ . By the end of the trial, 87% of the participants in the Active group (14) had achieved an equal or greater than 4.5-point reduction in CARS scores, only 35% of the participants of Sham group (5) achieved an equal or greater than 4.5-point reduction in CARS scores. The number of subjects that achieved this minimal clinically important difference in the Active group was statistically significantly higher compared to the Sham group. Therefore, the treatment was considered to have clinically meaningful efficacy.

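### The printed responder test (chi-square 8.48, p=.004) does not follow from the stated counts of 14/16 and 5/14, and the responder cut-off is worded two ways

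*SAP*

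**What the plan says.** The responder analysis is in the SAP under Primary Outcome. It is introduced as a count of children "whose change in CARS was greater than 4.5 points". The next sentence begins "The result was significant" and gives chi-square 8.48 with p=.004.

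The counts come after the test, and for a differently worded event: "87% of the participants in the Active group (14) had achieved an equal or greater than 4.5-point reduction in CARS scores", and "only 35% of the participants of Sham group (5) achieved an equal or greater than 4.5-point reduction in CARS scores".

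The same section gives group sizes of 16 (Active) and 14 (Sham) and states: "There were no missing CARS posttreatment evaluations". The analysis ends with: "Therefore, the treatment was considered to have clinically meaningful efficacy".

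The text available for review does not name the form of chi-square used or any continuity correction.

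**The concern.** There are two points.

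1. Everything needed to recompute the test is on the page, and the usual forms of the 2x2 chi-square do not return the printed value. Unless an adjusted test was used that the visible text does not describe, the statistic and the counts do not belong together.
2. The cut-off is strict (more than 4.5) where the analysis is defined and inclusive (4.5 or more) where the counts are given. The two rules differ for any child who changed by exactly 4.5 points, and the visible text does not say whether any child did.

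The sentence on clinically meaningful efficacy is drawn directly from this test. With 30 children, moving one or two of them across the cut-off changes the p-value visibly.

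**Working it through.** **Inputs (all from SAP, Primary Outcome).** Active n=16, responders 14. Sham n=14, responders 5. No missing post-treatment scores. Printed result: chi-square 8.48, p=.004.

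**Are the denominators right?** 14/16 = 87.5% and 5/14 = 35.7%. The printed 87% and 35% are these values truncated (rounded, they would be 88% and 36%). So 16 and 14 fit.

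**Is the printed pair consistent with itself?** Yes. A chi-square of 8.48 on 1 df has p=.0036, which rounds to .004.

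**Recomputation.** The table is [14, 2; 5, 9], with N=30, row totals 16 and 14, and column totals 19 and 11.

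- Cross-product difference: 14×9 − 2×5 = 116. Product of margins: 16×14×19×11 = 46,816.
- Pearson: 30 × 116² / 46,816 = 403,680 / 46,816 = 8.62.
- Yates: 30 × (116 − 15)² / 46,816 = 306,030 / 46,816 = 6.54.
- N-1: 8.6227 × 29/30 = 8.34.
- Likelihood ratio: 2 Σ O ln(O/E), with expected counts 10.13, 5.87, 8.87 and 5.13, gives 9.12.

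| Test on 14/16 vs 5/14 | Statistic | p |
|---|---|---|
| Printed | 8.48 | .004 |
| Pearson | 8.62 | .0033 |
| Yates | 6.54 | .011 |
| N-1 | 8.34 | .0039 |
| Likelihood ratio | 9.12 | .0025 |
| Cressie-Read | 8.71 | .0032 |
| Wald, log odds ratio | 7.27 | .0070 |
| Fisher exact | – | .0068 |

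N-1 matches the printed p after rounding, but its statistic is 8.34, so no row reproduces the pair. Pearson computed from the printed percentages (87% and 35%, with n=16 and 14) gives 8.64, so rounded inputs do not explain it either.

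**Could other counts give 8.48?** All 17 × 15 = 255 tables with arms of 16 and 14 were searched under Pearson, Yates, N-1 and likelihood ratio. None rounds to 8.48. The nearest, apart from mirror images, are Yates 8.4877 (14 vs 4 responders), Yates 8.4668 (13 vs 3) and Pearson 8.4381 (13 vs 4). Holding the responders at 14 and 5 and varying the denominators (Active 14 to 19, Sham 5 to 19) gives no match either.

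**Effect size on the stated counts.** Risk difference 0.875 − 0.357 = 0.518, or 52 points; Newcombe 95% CI 17 to 73.

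**What the cut-off could do.** The number of children at exactly 4.5 points is not given, so these tables are assumptions about what a strict rule would leave:

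| Responders, Active vs Sham | Pearson p | Yates p | Fisher p | Risk difference |
|---|---|---|---|---|
| 14 vs 5 (as stated) | .0033 | .011 | .0068 | 0.518 |
| 14 vs 4 | .001 | .0036 | .0022 | 0.589 |
| 13 vs 5 | .011 | .030 | .024 | 0.455 |
| 12 vs 5 | .030 | .072 | .063 | 0.393 |

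**The case against.** The strongest reply is that neither figure need be a slip. The statistic follows the strict wording and the counts follow the inclusive wording, so they may describe two different tables. If one Sham child changed by exactly 4.5 points, the strict table is 14/16 vs 4/14, and Yates is 30 × (132 − 15)² / 48,384 = 8.4877, p=.0036. Truncated, that is 8.48, and the percentages in the same section are truncated too. On this reading the strict rule gives the stronger result (Fisher .0022), and the weaker tables of 13 vs 5 and 12 vs 5 are not candidates, since they lie far from 8.48.

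This explanation is plausible but unconfirmed. It needs the statistic truncated while its p-value is rounded, and nothing in the documents says a Sham child sat on the cut-off. Even if it is true, the defect remains: the test and the counts printed beside it would rest on different rules.

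It is also fair to say that the analysis supplements the t-test on CARS change, which the SAP sets out under Primary Analyses, that the gap from Pearson is only 0.14, and that the test may be named in text not available for review. Those points limit the weight of the finding. They do not make 8.48 follow from 14/16 and 5/14.

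**Conclusion.** The concern holds on both counts. The printed statistic cannot be obtained from the stated counts under Pearson, Yates, N-1 or likelihood-ratio chi-square, and the cut-off has two wordings. Confidence is high on those two facts. The cause is not settled by the documents, and neither is whether the two points are linked.

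If the stated counts are right, the consequence is small: p runs from .0025 to .011 across the four chi-square forms, with Fisher at .0068, so the result stays below an assumed 0.05 level in the same direction. If a strict cut-off changes the counts, the result could strengthen or weaken. Under the least favourable assumption tried (two Active children and no Sham child at exactly 4.5) Fisher is .063, but nothing in the documents points to that case. This is a reporting error that should be corrected. On the stated counts it does not reverse the finding.

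**What to change.** - State one threshold, either more than 4.5 points or 4.5 points and above, and use it for both the counts and the test.
- Print the 2x2 table with denominators 16 and 14, and name the test and any continuity correction.
- Replace 8.48 and .004 with values recomputed from the individual CARS changes under that threshold. If 14/16 and 5/14 are confirmed, report Pearson 8.62, p=.003, or Fisher p=.007, with a risk difference of 52 points (Newcombe 95% CI 17 to 73) and percentages of 88% and 36%. If the chosen threshold changes the counts, report the matching table, test and interval instead.

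The cost is a few lines of re-analysis on existing data and one change of wording. The p-value may become slightly more or less favourable.

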**Transcranial Photobiomodulation for
reducing autism symptoms in
children.**

October 1, 2020

PROTOCOL TITLE:

Transcranial photobiomodulation for reducing autism symptoms in children.

PRINCIPAL INVESTIGATOR:

Name	[name]
Department	N/A
Phone Number	

CO-INVESTIGATORS:

Name	[name]
Department	N/A
[contact]

Name	[name], CFA, Esq.
Department	N/A
[contact]

1.0 Purpose of the study:

The purpose of this 8-week open label feasibility study is to assess the tolerability, safety and efficacy of Transcranial LED Therapy for language learning and reducing symptoms of autism in children.

The investigators propose to enroll up to 30 participants of both genders ages 24 months to 6 years who have been previously diagnosed with moderate to severe ASD by licensed professionals according to the Diagnostic and Statistical Manual of Mental Disorders, Fifth Edition (DSM-5) criteria for Autism Spectrum Disorder (ASD).

The hypothesis to be tested is that exposure to photobiomodulation and speech parsing program will reduce children's symptoms of autism, such as delays in language production and comprehension, anxiety, tantrums, limited eye-contact and improve responsiveness.

2.0 Background / Literature Review / Rationale for the study:

2.1 Background Science of Photobiomodulation and Rationale:

There are several studies that suggest that mitochondrial energy disturbance is an underlying mechanism of autism, for at least some of the children. Specifically, Weisman, Kelley, Bauman, Cohen, Murray, Mitchell and Kern (2008) looked at the medical records of 25 children diagnosed with autism and found that "Levels of blood lactate, plasma alanine, and serum ALT and/or AST were increased at least once in 76%, 36%, and 52% of patients, respectively". Furthermore, 2 out of those 25 people had rare mtDNA mutations. The authors concluded that at least for a subset of ASD children, mitochondrial disturbances in energy production could be the underlying mechanism. Furthermore, Giulilvi, Zhang, Omanska-Klusek, Ross-Intra, Hertz-Picciotto, Tasson and Pessach (2010), looked at biochemical markers of ASD kids (2-5yo), and concluded that ASD children are more likely to have Mitochondria dysfunction, mtDNA replication and mtDNA deletion than neurotypical ones.

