Once the program generates the random sequence of 30 participants (in the example above, the sequence goes 23, 25, 12, 15, etc), we will simply alternate the assignment to treatment and control conditions. For example, in the example above, participant number 23 is assigned to the treatment condition (1), and participant number 25 is assigned to the control condition (2). Because the sequence of the participants is randomized, the assignment to conditions is random.

7.5 Treatment: The treatment will take place twice a week for up to 30 minutes at a time.

During the study, while participants will be wearing the photobiomodulation device, they will be listening to the audio program, and they may be playing with their parent or the experimenter, using the toys of their choice (out of the many available in the experimenter’s office). The caregivers will be present during the experiment at all times. When the child and the parent arrive, they will be welcomed to the office, and introduced to the toys.

The child will be encouraged to play with toys and interact with the parent (or the experimenter). The children in the experimental condition will be asked to wear the device for no longer than 15 minutes. The children in the controlled condition will play for 30 minutes and wear the same device, without turning it on (the device won’t be turned on at that time). The total time in the office will be about 30 minutes (including playing).

If the child becomes uncomfortable, the parents will be able to leave the experiment without any punishment. No coercion or deception is involved in this study.

7.6 Pre and Post-Testing: CARS2 will be used for pretest and post-test. Please see attached a sample CARS 2 test. CARS 2 scores will be compared for analyses. **In addition, EEG will be collected from the participants in both Control and Experimental conditions pre and post -treatment (before Starting treatment in session 1 and in the end of treatment of Session 8). Mobile FDA approved EEG device Brain Scientific will be used to collect children's pre and post test EEG. There is no known danger of EEG collecting. In this study it will be using for measuring the efficacy treatment only.**

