7.7 On-going Data Collection: Parents will be asked to keep a daily diary of the child's behavior, specifically – words spoken, comprehension of instructions, eye contact, his sleep pattern, number of tantrums, anxiety, social interaction and eating. Qualitative data will be collected through short weekly interviews with the parents. These interviews can take place either in [name] office during the child's treatment or by phone. During those weekly interviews, the parents will be asked questions about their children's responsiveness to language, number of words they can produce, eye-contact, anxiety, frequency of tantrums, eating, and difficulties falling asleep and sleeping through the night. Please see attached proposed script for the weekly call. The qualitative data will be used to further inform and supplement quantitative data (total CARS 2 scores).

The study will collect qualitative and quantitative data. The quantitative data will be the total CARS2 scores of the participants of both Control and Treatment groups, obtained before and after the study is done. Mixed Design Analysis of Variance will be used to analyze quantitative data. **In addition, we will collect Before and After Prefrontal cortex EEG from the control and experimental treatment groups to measure electrophysiological changes in Prefrontal cortex. after treatment. EEG data will be analyzed (using Time-Frequency analysis), and after baseline normalization, the data will be used in aggregate to compare conditions numerically. The between group comparison before the treatment will be conducted using between subject T-test for each brainwave . The between group comparison will be conducted after treatment for each brain wave using between subject t-test. In addition, for the treatment condition only Before and After comparison will be conducted, using within subject t-test.** In addition, we will obtain qualitative data from weekly parental interviews, during which we will ask participants' parents about their children's behavior (see attached protocol). Qualitative data will be used for information purposes and will supplement quantitative data.

7.8 Blinding of the Researcher: [name] (the PI) will not be present in the room when the child is receiving the treatment. She will not be aware what group each particular participant has been placed in. [name] will be conducting the pre and post-testing interviews, as well as the on-going weekly interviews with the parents.

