## Data Collection and Statistical Analysis

### Primary Analyses

The last author, a licensed psychologist experienced in the use of CARS in clinical practice, conducted blinded Before and After CARS ratings for all participants. The final CARS evaluations were performed immediately after the final treatment session. CARS scores were analyzed using the independent sample t-test. We compared the differences from the baseline between both groups, calculating both the average difference and 95% CI within each group and between groups.

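### The SAP's claim of clinically meaningful benefit is drawn from a responder test that neither the protocol nor the SAP's Primary Analyses paragraph specifies, and that is not labelled exploratory

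*SAP*

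**What the plan says.** **Protocol.** The title page is dated "October 1, 2020". Section 7.6 states that "CARS 2 scores will be compared for analyses", and section 7.7 defines the outcome: "The quantitative data will be the total CARS2 scores of the participants of both Control and Treatment groups", taken before and after the study. The method follows: "Mixed Design Analysis of Variance will be used to analyze quantitative data". The protocol names no responder endpoint, CARS cut-off or minimal important difference.

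**SAP, Primary Analyses.** "CARS scores were analyzed using the independent sample t-test". The paragraph goes on to describe differences from baseline with 95% intervals within and between groups. It lists no responder analysis.

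**SAP, Primary Outcome.** The continuous result comes first: "The difference in the change in CARS between the two groups was 7.23 (95% CI 2.357 to 12.107", with a stated p of 0.01. An additional analysis then counts children "whose change in CARS was greater than 4.5 points", with the threshold attributed to a 2022 publication. The counts, given for reductions equal to or greater than 4.5, are 14 of 16 Active and 5 of 14 Sham, with chi-square 8.48 and p = .004. After noting that the counts differ significantly, the section closes: "Therefore, the treatment was considered to have clinically meaningful efficacy".

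**The concern.** The strongest statement in the SAP hangs on the analysis with the least visible planning. A cut-off credited to a 2022 source cannot have been taken from that source for a protocol dated 2020. The test first appears among the results, and the reader is not told when it was chosen. Without that date, its p-value cannot be read as if the error rate had been controlled in advance.

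There is also a gap in the inference that would remain even if the test had been planned. Rejecting equality of two responder proportions says that the proportions differ. It does not say by how much, and it does not show that the benefit attributable to treatment is large enough to matter. Only an estimate with its interval can address that, and the section gives none for the responder comparison.

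At stake is the wording of the trial's conclusion: whether a reader takes away a difference between groups, or an established and clinically important effect.

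**Working it through.** **1. What was planned.** Protocol 7.6 and 7.7 plan total CARS2, before and after, by mixed ANOVA. With two groups and two time points, the group-by-time test is equivalent to the pooled-variance t-test on change from baseline. The SAP's t-test on change is therefore the planned comparison in substance. The responder test is in neither plan.

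**2. The stated responder statistic.** Inputs (SAP, Primary Outcome): Active 14 responders and 2 non-responders; Sham 5 and 9.
- Pearson chi-square = N(ad − bc)² / (product of the margins) = 30 × (14×9 − 2×5)² / (16 × 14 × 19 × 11) = 8.62, p = 0.0033.
- With Yates correction: 6.54, p = 0.011. Fisher exact: p = 0.0068.
- None of these gives the stated 8.48; uncorrected Pearson is closest, 0.14 away. All are below 0.05, so nominal significance stands.
- The text uses a strict cut-off in one sentence and an inclusive one in the next. If the strict rule removed one Active responder (13/16 against 5/14), Pearson p = 0.011 and Fisher p = 0.024.

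**3. The responder result as an estimate.**
- Proportions: 14/16 = 0.875 and 5/14 = 0.357. Difference = 0.518.
- Wilson 95% limits: Active 0.640 to 0.965; Sham 0.163 to 0.612.
- Newcombe lower limit: 0.518 − √[(0.875 − 0.640)² + (0.612 − 0.357)²] = 0.518 − 0.347 = 0.171.
- Newcombe upper limit: 0.518 + √[(0.965 − 0.875)² + (0.357 − 0.163)²] = 0.518 + 0.214 = 0.731 with unrounded inputs.
- Result: 52 percentage points, 95% CI about 17 to 73.

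**4. The planned contrast.**
- From the stated means: (43.5 − 33.7) − (40.6 − 38.0) = 9.8 − 2.6 = 7.2, in line with the stated 7.23.
- SE from the stated interval, t on 28 df (2.048): (12.107 − 2.357) / (2 × 2.048) = 2.380.
- t = 7.23 / 2.380 = 3.04, two-sided p = 0.0051, which agrees with the stated 0.01 to two decimals.
- The interval excludes zero, so a group difference is supported without the responder test.

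**5. Illustrative comparison with 4.5.** The lower limit, 2.357, lies below 4.5; the point estimate, 7.23, lies above it. One-sided p for a mean difference above 4.5: t = (7.23 − 4.5) / 2.380 = 1.15, p about 0.13. The 4.5 points are applied in the SAP to each child's change, and such a threshold is not automatically one for a between-group mean difference.

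**The case against.** The best defence is that the SAP reports the planned analysis first, introduces the responder analysis as an addition, and discloses the Sham count. A published threshold is also less open to tuning than one the investigators set themselves. The planned contrast is significant on its own, so the evidence that the arms differ does not depend on the responder test. All of this stands. It limits the point to the claim of clinical importance.

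Three stronger readings are tempting, and the documents do not support them.

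- **That the cut-off was chosen after the data were seen.** The available SAP text is undated, part of the SAP was not available for review, and no date of unblinding or database lock is given. Specification after the protocol but before unblinding cannot be excluded. What can be said is that no such specification is shown.
- **That the responder result is fragile.** Removing two Active responders (12/16 against 5/14) gives Fisher p = 0.063, but Pearson, the type of test the SAP reports, gives p = 0.030. Nothing suggests that two children were misclassified.
- **That 5 of 14 Sham responders is itself a flaw.** A sham arm exists to measure that background rate. These children wore the unlit device, heard nursery rhymes and could receive behavioral therapy (Protocol 4.0 and 7.2), so they were not without any intervention.

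**Conclusion.** The point holds as a matter of analysis status and inference. The closing efficacy sentence follows from the significance of a responder test that is absent from the protocol's CARS analysis and from the SAP's Primary Analyses paragraph, with no label to tell the reader so.

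The planned comparison supports a difference between groups. The recalculated p-value assumes that the stated interval came from a t-test on 28 degrees of freedom; with as few as 15, it would still be about 0.006.

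A reader might go further and infer that the trial failed to reach a clinically important effect because the lower limit is about half of 4.5. That does not follow: the threshold is for individual change, and the point estimate exceeds it. The supported statement is that the size of the effect has not been established as clinically important, not that it has been shown to be unimportant. The mismatch in the chi-square value and the two versions of the cut-off do not reverse nominal significance in the cases checked.

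**What to change.** 1. Label the responder analysis as not pre-specified in the protocol and exploratory. If a dated specification made before unblinding exists, cite it instead.
2. Replace the closing efficacy sentence with a conclusion based on the planned between-group change: 7.23 points, 95% CI 2.357 to 12.107, p about 0.005, supporting a group difference.
3. Report responders as 14/16 against 5/14, a risk difference of 52 percentage points with Newcombe 95% CI about 17 to 73. Use one form of the cut-off throughout, and correct or explain the chi-square value.
4. If the mean difference is set against 4.5, say that the lower limit lies below it, that 4.5 is an individual-change threshold, and that the comparison is illustrative.

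Cost: rewording and one added interval, with no new data. The stated claim becomes less favourable.
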